If the assumption of normality is rejected for any of the above analyses, an appropriate transformation to the data will be performed to facilitate the method of analysis. In the absence of an appropriate data transformation, non-parametric

 GlaxoSmithKline	Document Name	SAP Amendment1		
	Type	Version	Document Identifier	Effective Date
	eldo_clinical_doc	1.0; CURRENT; Most-Recent; Effective	090032d580d52182	13-Jun-2017 06:57:54
	Reason For Issue	Auto Issue		

analyses will be performed. In the case of a non-parametric analysis, median differences will be presented, together with 95% confidence intervals based on the Hodges-Lehmann method.

Calculated AUC's are found by using values at time $T = t_1=0, t_2, \dots, t_k$ (real dates not nominal days) and changes from baseline values denoted by $\delta_1=0, \delta_2, \dots, \delta_k$; as the sum of, the area of each trapezium (above the horizontal line indicating the baseline value) and calculated as the width of the trapezium ($t_{j+1} - t_j$) multiplied by the average applicable δ 's (δ_{j+1}, δ_j) with the first δ , $\delta_1=0$. These are in fact areas over the baseline value (AOB). The AOB will be standardized by dividing by the overall width $t_k - t_1$ using real dates rather than nominal days.

Section: 9 Safety Analysis

Reason for amendment: Reference to additional pre-unblind step of assigning application site(s) AE's to treatment at that site(s). A textual field is recorded indicating such.

Original text: Treatment emergent AEs are defined as events that start on or after the first treatment date. Events occurring following the start of treatment which were also reported before treatment began with no change in severity or causality will however not be considered treatment emergent.

As per Section 7.1.1 of the protocol, the following does not constitute an AE:

- Any localised response to the D-Squame disc application and removal on the face and forearms, unless more severe than expected in which case will be captured as an AE.

AEs will be tabulated according to the current version of the MedDRA. Frequencies and percentages will be presented by product group and overall, for each system organ class, and for each preferred term. Summaries of treatment-emergent AEs, treatment-related treatment-emergent AEs, AEs leading to discontinuation, and serious AEs will be completed. AEs relating to the forearm or face will be summarized separately.

Amendment: Treatment emergent AEs are defined as events that start on or after the first treatment date. Events occurring following the start of treatment which were also reported before treatment began with no change in severity or causality will however not be considered treatment emergent.

 GlaxoSmithKline	Document Name	SAP Amendment1		
	Type	Version	Document Identifier	Effective Date
	eldo_clinical_doc	1.0; CURRENT; Most-Recent; Effective	090032d580d52182	13-Jun-2017 06:57:54
	Reason For Issue	Auto Issue		

As per Section 7.1.1 of the protocol, the following does not constitute an AE:

- Any localised response to the D-Squame disc application and removal on the face and forearms, unless more severe than expected in which case will be captured as an AE.

AEs will be tabulated according to the current version of the MedDRA. Frequencies and percentages will be presented by product group and overall, for each system organ class, and for each preferred term. Summaries of treatment-emergent AEs, treatment-related treatment-emergent AEs, AEs leading to discontinuation, and serious AEs will be completed. AEs relating to the forearm or face will be summarized separately.

A further step will take place pre-unblind to flag the AEs by application site if appropriate so that attribution to applied treatment is preserved. This will involve review of all application site AEs (including textual information) and addition of a flag to the clinical database to indicate which site(s) it is applicable to. Other whole body events will be attributed to both treatments received.

Document Name	SAP Amendment1		
Type	Version	Document Identifier	Effective Date
eldo_clinical_doc	1.0; CURRENT; Most-Recent; Effective	090032d580d52182	13-Jun-2017 06:57:54
Reason For Issue	Auto Issue		

SIGNATURE PAGE

SAP Amendment1

Date	Signed By
13-Jun-2017 06:00:28	PPD
Justification	Approved

Date	Signed By
13-Jun-2017 06:57:49	PPD
Justification	Biostatistics Approval

Date	Signed By
Justification	

Date	Signed By
Justification	

Date	Signed By
Justification	

Date	Signed By
Justification

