forearm.	treated and untreated sites on the forearm on Day 29.
To assess the levels of protein present on D-Squame discs following 4 weeks of using the test product from sites on the face.	Protein analysis of D-Squame discs following removal of 3, 6 and 9 adhesive discs from skin of both test product treated and untreated sites on the face on Day 29.
To assess skin barrier function on the forearm and face through a Regression Period following 4 weeks of test product use.	Change from baseline and from Day 29 in TEWL measurements on Days 30, 31, 32, 33 and 34 in test product treated site vs untreated sites on the forearm and face. As well as standardised AUCs calculated using change from baseline and from Day 29 in TEWL over regression period (Days 30, 31, 32, 33 and 34) at Area 1 and 3 (Forearm) and Area 6 and 8 (Face).
To assess moisturisation levels on the forearm and face through a Regression Period following 4 weeks of test product use.	Change from baseline and from Day 29 in Corneometry measurements on Days 30, 31, 32, 33 and 34 in test product treated site vs untreated site on the forearm and face. As well as Standardised AUCs calculated using change from baseline and from Day 29 in corneometry over regression period (Days 30, 31, 32, 33 and 34) at Area 1 and 3 (Forearm) and Area 6 and 8 (Face).
Validation of trial with respect to skin barrier function on the forearm after 4 weeks via comparison of the positive control to no treatment.	Change from baseline in TEWL measurements on Day 29 of test product treated site vs untreated site on the forearm (Area 1 and 3).
To evaluate the local tolerance.	Frequency and severity of Adverse Events.

3 Study Design

[figure not shown]
- Evaluator-blind
- Single study center
- Split-body
- Healthy female subjects aged 18 to 65 with self-reported dry, sensitive skin on their face and body

	Document Name	Statistical Analysis Plan.docx		
	Type	Version	Document Identifier	Effective Date
	eldo_clinical_doc	1.0; CURRENT; Most-Recent; Effective	090032d580d11909	21-Mar-2017 07:37:11
	Reason For Issue	Auto Issue		

[figure not shown]
- Positive- (Olay ProX Wrinkle Smoothing Cream) and Untreated-control
- Randomization was to two of the 3 treatment arms (test product, positive control, no treatment) with treatment arm assignment further randomized to either the right side or left side of the body. Therefore, a subject was randomized to one of the 6 possible treatment groups:

Right Side of Body	Left Side of Body

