Appendix 3 Templates for Tables, Figures & Listings

 GlaxoSmithKline	Document Name	Statistical Analysis Plan.docx		
	Type	Version	Document Identifier	Effective Date
	eldo_clinical_doc	1.0; CURRENT; Most-Recent; Effective	090032d580d11909	21-Mar-2017 07:37:11
	Reason For Issue	Auto Issue		

Protocol No. 207451

Page x of y
 Program Run Date:xxxx

Table 9.3.1.1.1
 Summary of Forearm TEWL
 ITT Population (N=xx)

Timepoint		Moisturising Cream	Olay ProX Cream	No Treatment
Baseline*	N	XX	XX	XX
	Missing	XX	XX	XX
	Mean	X.XX	X.XX	X.XX
	SD	X.XXX	X.XXX	X.XXX
	95%CI	X.XX, X.XX	X.XX, X.XX	X.XX, X.XX
Day 2	N	XX	XX	XX
	Missing	XX	XX	XX
	Mean	X.XX	X.XX	X.XX
	SD	X.XXX	X.XXX	X.XXX
	95%CI	X.XX, X.XX	X.XX, X.XX	X.XX, X.XX
Day 2 Change from Baseline	N	XX	XX	XX
	Missing	XX	XX	XX
	Mean	X.XX	X.XX	X.XX
	SD	X.XXX	X.XXX	X.XXX
	95%CI	X.XX, X.XX	X.XX, X.XX	X.XX, X.XX
	LSMean (±SE) [#]	X.XX (X.XXX)	X.XX (X.XXX)	X.XX (X.XXX)
	LSMean 95%CI	X.XX, X.XX	X.XX, X.XX	X.XX, X.XX
	P-value	X.XXX	X.XXX	X.XXX
Day 15	N	XX	XX	XX

	Document Name	Statistical Analysis Plan.docx		
	Type	Version	Document Identifier	Effective Date
	eldo_clinical_doc	1.0; CURRENT; Most-Recent; Effective	090032d580d11909	21-Mar-2017 07:37:11
	Reason For Issue	Auto Issue		

	Missing	XX	XX	XX
	Mean	X.XX	X.XX	X.XX
	SD	X.XXX	X.XXX	X.XXX
	95%CI	X.XX, X.XX	X.XX, X.XX	X.XX, X.XX
Day 15 Change from Baseline	N	XX	XX	XX
	Missing	XX	XX	XX
	Mean	X.XX	X.XX	X.XX
	SD	X.XXX	X.XXX	X.XXX
	95%CI	X.XX, X.XX	X.XX, X.XX	X.XX, X.XX
	LSMean (\pm SE) [#]	X.XX (X.XXX)	X.XX (X.XXX)	X.XX (X.XXX)
	LSMean 95%CI	X.XX, X.XX	X.XX, X.XX	X.XX, X.XX
	P-value	X.XXX	X.XXX	X.XXX
Day 29	N	XX	XX	XX
	Missing	XX	XX	XX
	Mean	X.XX	X.XX	X.XX
	SD	X.XXX	X.XXX	X.XXX
	95%CI	X.XX, X.XX	X.XX, X.XX	X.XX, X.XX
Day 29 Change from Baseline	N	XX	XX	XX
	Missing	XX	XX	XX
	Mean	X.XX	X.XX	X.XX
	SD	X.XXX	X.XXX	X.XXX
	95%CI	X.XX, X.XX	X.XX, X.XX	X.XX, X.XX
	LSMean (\pm SE) [#]	X.XX (X.XXX)	X.XX (X.XXX)	X.XX (X.XXX)
	LSMean 95%CI	X.XX, X.XX	X.XX, X.XX	X.XX, X.XX
	P-value	X.XXX	X.XXX	X.XXX

	Document Name	Statistical Analysis Plan.docx		
	Type	Version	Document Identifier	Effective Date
	eldo_clinical_doc	1.0; CURRENT; Most-Recent; Effective	090032d580d11909	21-Mar-2017 07:37:11
	Reason For Issue	Auto Issue		

AUC Change from Baseline Days 2 through 29	N	XX	XX	XX
	Missing	XX	XX	XX
	Mean	X.XX	X.XX	X.XX
	SD	X.XXX	X.XXX	X.XXX
	95%CI	X.XX, X.XX	X.XX, X.XX	X.XX, X.XX
	LSMean (\pm SE) [#]	X.XX (X.XXX)	X.XX (X.XXX)	X.XX (X.XXX)
	LSMean 95%CI	X.XX, X.XX	X.XX, X.XX	X.XX, X.XX

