Standardised AUCs will be calculated for each subject for change from baseline in TEWL and corneometry (Area 1 and 3 on the forearms and Area 6 and 8 on the face) over the treatment period; i.e. through Day 29 (Days 1, 2, 15, and 29) and separately over the Regression period; i.e. through Day 34 (Days 30, 31, 32, 33 and 34) using the trapezoidal rule and dividing by the number of days in the period. Each of the treatment period and regression period AUCs will be similarly summarized and compared for both the forearm and face using analysis of covariance (ANCOVA) with subject as a random effect, treatment arm (test product, positive control and no treatment) and side of body treatment applied (right, left) as main effects and baseline value as covariate. Least square means from the ANCOVA model for the change from baseline will be presented for each treatment arm and for the difference between each pair of the active treatment arms and no treatment together with p-values and 95% confidence intervals. **In case of any individual subject missing**

 GlaxoSmithKline	Document Name	SAP Amendment1		
	Type	Version	Document Identifier	Effective Date
	eldo_clinical_doc	1.0; CURRENT; Most-Recent; Effective	090032d580d52182	13-Jun-2017 06:57:54
	Reason For Issue	Auto Issue		

values between Day 1 and Day 29 the AUC(1-29) will not be calculated for those subjects, and if any of Day29 to Day 34 are missing the AUC(29-34) will not be calculated for those subjects.

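### Amendment 1's single AUC formula forces the first change to zero, which is wrong for the regression-period AUC of change from baseline, and the AUC intervals are labelled inconsistently

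*SAP*

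**What the plan says.** **Formula.** The AUC paragraph that closes the amended Section 8.2 works with "values at time $T = t_1=0, t_2, \dots, t_k$ (real dates not nominal days", and defines the accompanying values as changes from baseline. Each trapezium is its width times the average of its two changes, and the sum is divided by the last time minus the first. The first change is set to zero twice, the second time as "\delta_1=0$. These are in fact areas over the baseline value (AOB". No period or endpoint is excepted.

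**Endpoints it must serve.** Section 2 lists, for the regression period, "standardised AUCs calculated using change from baseline and from Day 29 in TEWL over regression period (Days 30, 31, 32, 33 and 34" and "Standardised AUCs calculated using change from baseline and from Day 29 in corneometry over regression period (Days 30, 31, 32, 33 and 34". So two AUCs are planned over the same days, with different reference values, for each measure and body area. The amended Section 8.2 repeats the change-from-baseline version.

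**Regression interval.** The amended Section 8.2 computes this AUC "separately over the Regression period; i.e. through Day 34 (Days 30, 31, 32, 33 and 34", and the Appendix 3 shells also label it Days 30-34. The missing-data sentence in the same paragraph reads "if any of Day29 to Day 34 are missing the AUC(29-34) will not be calculated for those subjects".

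**Treatment interval.** The amended Section 8.2 uses Days 1, 2, 15 and 29, and its missing-data rule concerns "values between Day 1 and Day 29 the AUC(1-29) will not be calculated for those subjects". Shell Table 9.3.1.1.1 has "AUC Change from Baseline Days 2 through 29", and Table 9.3.1.1.2 likewise has Days 2-29. Amendment 1 does not revise Appendix 3, so these shells remain in force.

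**The concern.** A first change of zero is an identity only when the interval begins at the point from which change is measured. The regression-period AUC of change from baseline begins about four weeks after its reference point, and its first ordinate is the effect present when treatment stops. Replacing that with zero discards an observed value and pulls the AUC, and the expected between-arm difference, toward no effect. These AUCs are the summary measures of how long the effect lasts after stopping.

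The labels add a second problem. If the effect fades, an AUC starting at Day 29 differs from one starting at Day 30 even with the zero corrected. The start also governs who is included. The amended Section 5.4 voids an AUC only when a contributing value is missing, so with a Day 30 start a subject missing only Day 29 keeps her change-from-baseline AUC. Under the Section 8.2 missing-data rule she loses it. Two programmers could each follow the SAP and report different values on different numbers of subjects.

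**Working it through.** The SAP states no AUC figure, so there is none to reproduce. The check applies the SAP's formula with the first change observed and with it set to zero.

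**Inputs.** Days 29-34 (missing-data rule) or Days 30-34 (Section 2, Section 8.2 text, shells), at one-day spacing. The profiles are assumptions, expressed as multiples of the Day 29 change *c*: constant; linear fade to half by Day 34; linear fade to zero by Day 34.

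**Formula.** AUC = Σ (t_{j+1} − t_j)(δ_j + δ_{j+1})/2 ÷ (t_k − t_1). Setting δ_1 = 0 removes ½(t_2 − t_1)δ_1 ÷ (t_k − t_1), which is 0.5·δ_1/5 for Days 29-34 and 0.5·δ_1/4 for Days 30-34.

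| Profile | 29-34: observed → zeroed | Loss | 30-34: observed → zeroed | Loss |
|---|---|---|---|---|
| Constant | 1.00 → 0.90 | 10% | 1.00 → 0.875 | 12.5% |
| Fade to half | 0.75 → 0.65 | 13% | 0.70 → 0.5875 | 16% |
| Fade to zero | 0.50 → 0.40 | 20% | 0.40 → 0.30 | 25% |

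Example, fade to zero, Days 30-34: the changes are 0.8, 0.6, 0.4, 0.2, 0. Observed: (0.4 + 0.6 + 0.4 + 0.2 + 0)/4 = 0.40. Zeroed: (0 + 0.6 + 0.4 + 0.2 + 0)/4 = 0.30. On the scale of the 1.5-point difference in Section 4, a constant effect is reported as 1.35 (Days 29-34) or 1.31 (Days 30-34).

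**Test statistic.** Zeroing also removes some variance, so power falls less than the estimate does. Take AUC divided by its standard error, with equal variances and a common between-day correlation ρ. With trapezoid weights w, the variance is proportional to (1 − ρ)Σw² + ρ(Σw)². The change in the statistic, for ρ = 0, 0.5, 0.8 and 1, is:

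| Profile | Days 29-34 (%) | Days 30-34 (%) |
|---|---|---|
| Constant | −7.4, −1.2, −0.4, 0.0 | −9.2, −1.9, −0.5, 0.0 |
| Fade to half | −10.8, −4.9, −4.0, −3.7 | −12.9, −5.9, −4.6, −4.1 |
| Fade to zero | −17.7, −12.2, −11.4, −11.1 | −22.2, −15.9, −14.8, −14.3 |

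**Start day, observed first values.** Day 30 against Day 29: 1.00 v 1.00 (0%), 0.70 v 0.75 (−7%), 0.40 v 0.50 (−20%).

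**Treatment-period label.** For a constant effect from Day 2, Days 1-29 give (0.5 + 13 + 14)/28 = 0.982c. Days 2-29 give 27/27 = 1.000c with the observed first value, but (6.5 + 14)/27 = 0.759c if the shell interval is combined with a first change of zero.

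**Change from Day 29.** For a linear return to −c by Day 34, a Day 29 start gives −0.500c. A Day 30 start gives −0.600c observed and −0.575c zeroed. The zero is therefore right for this AUC only if it starts at Day 29.

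**The case against.** The strongest reply is that the formula describes a curve starting at its own reference point, with time zero at baseline, and was never meant to overwrite an observed Day 29 or Day 30 value. A sensible programmer might read it so. But the text does not limit itself to such curves; it covers all the AUCs and repeats the zero. Taking time zero literally as Day 1, followed by Days 30-34, does not rescue it. A straight line from Day 1 to Day 30 then enters the area, and a constant effect gives (14.5 + 4)/33 = 0.561c. The 10% to 25% range belongs to the reading in which the zero falls on the first day of the regression interval.

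It can also be said that Section 8.2 already settles a missing Day 29, since its rule requires that day. The rule is written down, but it contradicts the amended Section 5.4 if the interval is Days 30-34. The shells predate the amendment, and Days 2-29 may only list post-baseline TEWL visits. That explains the label without resolving it, because the amended paragraph itself still says Days 30-34 for the regression period.

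What stands is the limit on impact. At a between-day correlation of 0.5 or more, the test statistic loses at most about 6% unless the effect fades further than half. The AUC/SE calculation is simpler than the planned ANCOVA. Success rests on Day 29 forearm TEWL, p-values are treated mainly as summary statistics, and Days 30 to 34 are each compared separately.

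**Conclusion.** The concern holds. As written, the rule gives a wrong value for the regression-period AUC of change from baseline, for TEWL and corneometry on forearm and face. The standardised AUC is understated by 10% to 20% (Days 29-34) or 12.5% to 25% (Days 30-34) across the three profiles. The test statistic changes by between 0% and −18%, or between 0% and −22%, depending on profile and between-day correlation. These sizes rest on assumed profiles, one-day spacing and equal variances, none of which the SAP supplies. That the first value is not zero by definition does not depend on them.

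The interval conflicts are a separate, real fault: with observed first values, the choice of start day alone moves the AUC by 0% to −20%. The primary analysis and the day-by-day regression comparisons are untouched. This should be corrected, but it does not threaten the study's main conclusion.

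**What to change.** In the amended Section 8.2, define each AUC separately:

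- **Treatment period, change from baseline:** starts at Day 1, first change zero.
- **Regression period, change from Day 29:** starts at Day 29, first change zero. The Days 30-34 labels for this AUC must change accordingly, because the zero is not true at Day 30.
- **Regression period, change from baseline:** first value is the observed change from baseline on the first day of the interval. The sponsor should choose one start, Day 30 as in Section 2, the Section 8.2 text and the shells, or Day 29 as in the missing-data rule.

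Divide each by its own last time minus first time on real dates, and let this replace the text's division by the number of days in the period. Then align the Section 2 endpoints, the Section 8.2 text, the missing-data rules in Sections 5.4 and 8.2, and the Appendix 3 shells, correcting Days 2-29 to Days 1-29.

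The cost is a few lines of SAP and shell text. Data collection, sample size and the primary analysis do not change.
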